13.2 Primary Efficacy Analysis

The primary efficacy endpoint of the study, chemical composition of the dialysis solution from the simulated treatment, will be analyzed descriptively using frequencies and percentages of those that meet specifications vs those that do not.

The dialysis solution will be considered as meeting specifications if all of the below parameters are within the specified limits:

Parameter	Limits
pH at 25°C	4.0 to 6.5
Color	≤ 15
5-HMF	≤ 0.25

Dextrose Hydrous Assay:	
1.5% Dextrose, Hydrous	1.40 to 1.60
2.5% Dextrose, Hydrous	2.38 to 2.62
4.25% Dextrose, Hydrous	4.00 to 4.50
Sodium Lactate (g/L)	4.23 to 4.73
Sodium (mEq/L)	125 to 139
Chloride (g/L)	5.28 to 5.83
MgCl ₂ 6H ₂ O (g/L)	0.041 to 0.061
CaCl ₂ 2H ₂ O (g/L)	0.157 to 0.210

If any one of the above parameters tested fall outside of the limits given, then the particular test is considered not meeting specifications. If any of the above parameters were not tested, then the particular test is considered missing. All testing for dialysis solution will be completed at the Baxter Round Lake laboratory facility.

The testing of the dialysis solution occurs four times throughout the trial: once at simulated treatment (week 1), and once at each of the treatment visits (weeks 4, 8, and 12). The Dextrose Hydrous % will be set to the following for each of the weeks: 1.5% at weeks 1 and 12, 2.5% at week 4, and 4.25% at week 8.

There will be three summaries of these data: one based on initial values, one based on retest values (as mandated per decision tree), and one based on the most recent test values. These three summaries will be done on a combination of all visits and individually for each of the visits.

In addition to the above, there will be two additional tables detailing the chemical composition of the dialysis solution. The first will show the test results (met vs did not meet specifications) for each of the individual parameters, and the second will be a descriptive summary (n, mean, standard deviation, minimum, median, and maximum) of the results of each of the individual parameters.

If a patient had been re-enrolled in the study, all data will be gathered and summarized for this analysis.

The test results will also be listed. Patient's age, sex, race, and weight at baseline will not be shown for this listing. This listing will include all enrolled patients.

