**Table 2. Composition of Electrolyte Concentrate**

Component	Component Quantity	
	Quality Standard	g/L (nominal)
Calcium Chloride, Dihydrate	USP	3.675
Magnesium Chloride, Hexahydrate	USP	1.017
Sodium Chloride	USP	107.5
Sodium Lactate Solution	USP	89.65
Water for Injection	USP/EP	QS

USP = United States Pharmacopeia; EP = European Pharmacopoeia; QS = Quantity sufficient

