**Table 3. Composition of the AMIA APD Generated Solution (mmol/L)**

Component	1.5% Dextrose	2.5% Dextrose	4.25% Dextrose
Dextrose	75.5	126	214
Sodium	132	132	132
Calcium	1.25	1.25	1.25
Magnesium	0.25	0.25	0.25
Chloride	95	95	95
Lactate	40	40	40
pH	~ 6	~ 6	~ 6

The AMIA APD Concentrates, after dilution by the AMIA APD Solution Generation System, are indicated for adult patients in acute or chronic renal failure when non-dialytic medical therapy is judged to be inadequate.

- The AMIA APD Concentrates are only intended to be used together, and only as a part of the AMIA APD Solution Generation System.
- The Dextrose Concentrate is a sterile, non-pyrogenic product used in the preparation of the AMIA APD Generated Solution when using the AMIA APD Solution Generation System.
- The Electrolyte Concentrate is a sterile, non-pyrogenic product containing the electrolytes and buffer used in the preparation of the AMIA APD Generated Solution when using the AMIA APD Solution Generation System.

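### The chloride limits in the primary efficacy specification table (SAP 13.2) cannot be met as labelled; they fit the 95 mmol/L target only if read as total chloride expressed as NaCl

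*SAP*

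**What the plan says.** SAP 13.2 lists the limits that a sample of generated solution must satisfy. The chloride row reads "Chloride (g/L) 5.28 to 5.83". The other electrolyte rows are "Sodium (mEq/L) 125 to 139", "Sodium Lactate (g/L) 4.23 to 4.73", magnesium chloride hexahydrate "0.041 to 0.061" g/L and calcium chloride dihydrate "0.157 to 0.210" g/L. The decision rule is all-or-nothing: "If any one of the above parameters tested fall outside of the limits given, then the particular test is considered not meeting specifications".

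The target composition is in the protocol. Table 3, in mmol/L, gives "Chloride 95 95 95" for the three dextrose strengths, and Appendix 3 gives the same 95 mmol/L for Dianeal Low Calcium. Table 2 gives the electrolyte concentrate, including "Sodium Chloride USP 107.5" g/L. Neither document says that the chloride limits are expressed as sodium chloride, and neither gives the unit in which the laboratory reports chloride.

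**The concern.** The chloride row is the only electrolyte row with a stated nominal value that its limits, read as labelled, do not contain. Elsewhere the SAP states an expression basis where one applies. The lactate, calcium and magnesium rows of this table name the salt, and the nitrate rows in SAP 14.1.2 and 14.3.5 say that nitrate is counted as nitrogen. An unqualified chloride row in g/L therefore reads as chloride ion.

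The row is a threshold of the primary efficacy endpoint, and failing it fails the whole test. Anyone who programs or reproduces the pass/fail flag from the SAP alone could class every on-target sample as not meeting specification.

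**Working it through.** **Inputs.** Limits are from SAP 13.2. Targets and salt contents are from Protocol Tables 2 and 3 and Appendix 3. Molar masses (g/mol) are standard constants, not taken from the documents: Cl 35.453, NaCl 58.443, CaCl2·2H2O 147.01, MgCl2·6H2O 203.30, sodium lactate 112.06.

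**1. Reproduce the 95 mmol/L target.**
- Appendix 3 salts: 1000 × (5.38/58.443 + 2 × 0.183/147.01 + 2 × 0.051/203.30) = 95.05 mmol/L. The same salts give sodium 132.03 and lactate 39.98 mmol/L, matching the stated 132 and 40.
- Table 2 concentrate: 107.5/58.443 + 2 × 3.675/147.01 + 2 × 1.017/203.30 = 1.8994 mol/L. Divided by 20, the factor that reproduces Appendix 3, this is 94.97 mmol/L.

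The target is sound. As chloride ion it is 95 × 35.453/1000 = 3.37 g/L.

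**2. Read the SAP row as labelled (chloride ion).**
- 5.28/35.453 × 1000 = 148.9 mmol/L; 5.83/35.453 × 1000 = 164.4 mmol/L.
- An on-target sample falls short of the lower limit by 1 − 3.368/5.28 = 36.2%.

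**3. Test the row against the rest of its own table.** Chloride cannot exceed the total positive charge. With each cation at its SAP upper limit:
- sodium: 139 mEq/L
- calcium: 2 × 0.210/147.01 × 1000 = 2.86 mEq/L
- magnesium: 2 × 0.061/203.30 × 1000 = 0.60 mEq/L
- sum: 142.46 mEq/L, so chloride ion is at most 142.46 × 35.453/1000 = 5.05 g/L

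That is below 5.28 g/L with no lactate at all. Adding potassium at the 8 mg/L product-water limit (SAP 14.1.2) and hydrogen ion at pH 4.0 raises the sum only to 142.76 mEq/L, or 5.06 g/L. The table also requires lactate: 4.23/112.06 × 1000 = 37.7 mmol/L at minimum. Treated as fully ionised, this lowers the chloride ceiling to 142.46 − 37.75 = 104.7 mmol/L, about 3.71 g/L.

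**4. Look for a reading that fits.**

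| Reading of 5.28 to 5.83 g/L | Nominal value on that basis | Position of nominal |
|---|---|---|
| Chloride ion | 3.37 g/L | 36% below the lower limit |
| NaCl ingredient only (Appendix 3) | 5.38 g/L | Inside but off-centre: 1.9% above the lower limit, 7.7% below the upper |
| Total chloride expressed as NaCl | 95 × 58.443/1000 = 5.55 g/L | Central: midpoint of limits is (5.28 + 5.83)/2 = 5.555 |

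On the last reading the limits are 5.28/58.443 × 1000 = 90.3 and 5.83/58.443 × 1000 = 99.8 mmol/L, about ±5% around 95. As ion mass they are 3.20 to 3.54 g/L.

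**5. Compare the other rows.** Midpoints against nominal values: sodium 132 and 132; sodium lactate 4.48 and 4.48; MgCl2·6H2O 0.051 and 0.051; CaCl2·2H2O 0.1835 and 0.183; dextrose 1.50, 2.50 and 4.25 at the three strengths. The pH limits equal the Appendix 3 range. Color and 5-HMF have no stated nominal. Centred limits are the table's pattern, and chloride follows it only on the as-NaCl basis.

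**6. Size if applied literally to ion results.** 30 completers × 4 visits = 120 initial tests; 50 enrolled × 4 = 200. No on-target test would pass. Retests and re-enrolments would add to these denominators.

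**The case against.** The strongest reply is that this is a missing label, not a wrong limit. The numerals fit total chloride as NaCl almost exactly, and most neighbouring g/L rows are salt assays. The charge-balance argument proves the same label error a second time; it is not a second defect. All of that stands.

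Harm also needs two things to happen together: ion-based reporting and literal application of the row. SAP 13.2 places the testing at the sponsor's own laboratory, against the sponsor's own specification, and nothing in the documents suggests that the two use different bases. The zero-pass count is thus a conditional worst case. It would also be conspicuous. Protocol 6.5.8 provides real-time review and a sponsor committee review at least every two weeks, 6.5.8.5 sends out-of-specification results to decision trees, and SAP 13.2 tabulates each parameter separately. A silently wrong primary result is unlikely. Finally, the study is descriptive, with no hypothesis test or success threshold, and adding the basis would leave the numerals unchanged.

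This limits the likely consequence but does not repair the row. The basis appears nowhere in either document. Review during the study might reveal the mismatch but would not correct the SAP. A clarification made because every sample had failed would be a change to how a primary-endpoint limit is read after the results were known, even with the same numerals.

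**Conclusion.** The concern holds. As labelled, the row conflicts with the stated 95 mmol/L target (an on-target sample is 36% below the lower limit) and cannot be met together with the table's own sodium, calcium and magnesium limits (ceiling 5.05 g/L, floor 5.28 g/L). These two results rest only on the documents' figures, standard molar masses and charge balance.

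That the limits were meant as total chloride expressed as NaCl is a strong inference from the arithmetic, not something the documents state. The effect on results depends on the laboratory's reporting unit, which is not given: none if chloride is reported as NaCl, but no on-target test passing if chloride ion is reported in g/L, or converted from mmol/L with 35.45, and the row is applied as written. Because this is a pass/fail limit of the primary efficacy endpoint, it must be corrected whichever of these applies.

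**What to change.** Check the row against the sponsor's Dianeal Low Calcium specification and restate it in the SAP before database lock. If the inferred basis is confirmed, label the row as total chloride expressed as NaCl, 5.28 to 5.83 g/L, or give the same limits in ion units: about 90.3 to 99.8 mmol/L, or 3.20 to 3.54 g/L as chloride. Next to the table, state the unit in which the laboratory reports chloride and the conversion, if any, used to derive the pass/fail flag.

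The cost is one row of SAP wording and one query to the laboratory. No new data are needed.

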13.3 Secondary Efficacy Analysis

Total Kt/V_{urea} will be summarized descriptively for baseline and the Total Kt/V_{urea} visit (occurring one time during week 5, 6, 7 or 8 of the Study Treatment Period). Change from baseline will also be summarized. For patients who re-enroll, if the baseline value is the same for each enrollment instance, then the baseline value will be summarized only once. If the baseline value is different, then each baseline value will be summarized. All available mid-treatment values and corresponding changes from baseline will be analyzed. A listing with these values will also be created.

14. SAFETY AND TOLERABILITY

14.1 Primary Safety Analysis

14.1.1 General Considerations

Unless otherwise specified, only data required per protocol (specified visits and retests per decision trees) will be displayed in summary tables. All data (including unscheduled visits, non-protocol mandated samples, etc.) will be displayed in listings.

For all device related endpoints, the results at each visit will be representative of the number of weeks the water device has been in use (i.e. visit 2 represents 8 weeks of use for that specific water device). Therefore, if a patient received a new water device midway through the study, the number of weeks in use would restart from 1.

14.1.2 Microbiological and chemical contamination testing of the product water from the WD (pre-sterilizing filter)

The results of the microbiological and chemical contamination testing of the product water from the WD will be analyzed descriptively using frequencies and percentages of those that meet specifications vs those that do not. A test will be considered meeting specifications if all of the following parameters fall within the specified limits:

Parameter	Limits
TAMC (CFU/mL)	≤ 100
TYMC (CFU/mL)	≤ 100
Endotoxins (EU/mL)	≤ 0.25
Aluminum (mg/L)	≤0.01
Copper (mg/L)	≤0.1
Fluoride (mg/L)	≤0.2
Lead (mg/L)	≤0.005
Nitrate (as N) (mg/L)	≤2

Sulphate (mg/L)	≤100
Zinc (mg/L)	≤0.1
Calcium (mg/L)	≤2
Magnesium (mg/L)	≤4
Potassium (mg/L)	≤8
Sodium (mg/L)	≤70
Antimony (mg/L)	≤0.006
Arsenic (mg/L)	≤0.005
Barium (mg/L)	≤0.1
Beryllium (mg/L)	≤0.0004
Cadmium (mg/L)	≤0.001
Chromium (total) (mg/L)	≤0.014
Mercury (mg/L)	≤0.0002
Selenium (mg/L)	≤0.09
Silver (mg/L)	≤0.005
Thallium (mg/L)	≤0.002
Nickel (mg/L)	≤0.010
Cobalt (mg/L)	≤0.0025
Total Chlorine (mg/L)	≤0.1

If any of the above parameters fall outside the limits, then the test is considered not meeting specifications. If any of the above parameters were not tested, then the particular test is considered missing. The microbiological tests are performed at [REDACTED], and the chemical contamination tests are performed at [REDACTED].

There will be three summaries of these data: one based on initial values, one based on retest values (as mandated per decision tree), and one based on the most recent test values. These three summaries will be done on a combination of all visits and individually for each of the visits.

In addition to the above, there will be two additional tables detailing the microbiological and chemical contamination testing of the product water from the water device. The first will show the test results (met vs did not meet specifications) for each of the individual parameters, and the second will be a descriptive summary (n, mean, standard deviation, minimum, median, and maximum) of the results of each of the individual parameters.

If a patient had re-enrolled, all data will be used in this analysis.

The test results will also be listed. Patient’s age, sex, race, and weight at baseline will not be shown for this listing. This listing will include all enrolled patients.

A sensitivity analysis will be conducted for this endpoint using the results of the home installation visit in cases where the simulation visit 1 data is missing. The sensitivity analysis will include all of the above tables only.

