### **6.5.8 Water and Dialysate Sampling Analysis**

Feed water used to supply the WD will be collected by Baxter personnel and sent for analysis during the home assessment process and again at the de-installation visit. Feed water shall not exceed the chemical or biological contaminant levels as stated in the AMIA APD Solution Generation System feed water specification and Feed Water Sampling at Installation for PoC APD. The product water from the WD (pre-sterilizing filters) shall conform to ISO 13959 for microbiological (including endotoxin) and chemical contamination, and the water in the holding bag (post-sterilizing filters) shall not exceed 0 CFU/mL for bacteria (no growth) and be < 0.03 EU/mL for endotoxins, consistent with Dianeal specifications for sterility. Product water shall not exceed the nitrate contamination limit of 2 mg/L. Sampling for product water testing for microbiological and chemical contamination may be done on different days within the allocated window.

The Sponsor or its designee will train the site nurses responsible for collecting the water and dialysate samples during the study. Instructions will be provided in the study training materials. Standardized recovery methods and controls will be incorporated into the testing protocol(s). Central laboratories will be used for all water and dialysate testing.

---

Sample results will be sent to the study sites and Sponsor for real time review and action (if appropriate). Observations and decisions regarding corrective measures (e.g., re-culture and/or disinfection of the WD) will be based on the organism growing and on whether bacterial or endotoxin levels exceed the specified guidelines. An internal Sponsor Committee will also review study wide results on a bi-weekly basis, at a minimum, to search for trends and to action appropriately.

Analysis of water will be performed on samples obtained as follows.

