-------------	-----------------------------	--	--	---------------------------------	--	---	------------------------------	--

u Microbiological (including endotoxin) and chemical testing of product water produced in the home will occur after the installation of the AMIA APD Solution Generation System. Simulated treatments will occur during week 1, before the first treatment in the home with the AMIA APD Solution Generation System, and during Study Treatment Weeks 4, 8 and 12. The dialysis solution generated by the simulated treatment will be collected from the system in the heater bag and used to evaluate the chemical composition of the final dialysis solution. Product water from the WD (pre-sterilizing filters) will be collected and tested to confirm that it conforms to ISO standard 13959 for microbiological (including endotoxin) and chemical contamination, and water from the holding bag (post-sterilizing filters), generated during a simulated treatment, will be collected and tested to confirm it does not exceed 0 CFU/mL for bacteria (no growth) and is < 0.03 EU/mL for endotoxins, consistent with Dianeal specifications for sterility. The simulated treatment will occur in addition to the patient’s normal therapy regimen (except at the last Simulated Treatment Visit, which is conducted after the last treatment). Patients will be required to use new AMIA APD Concentrates and disposable sets for their PD treatment. The chemical collection test sampling may occur on a different day than the product water microbiological test sampling.

v Tests carried out during Screening are for safety checks prior to therapy and will not be used in the analysis.

w Collection of AMIA APD Solution Generation System-related product complaints and device deficiencies, which would include functional characteristics (e.g., particulate matter, PD fluid discoloration, leaks, tubing separations), will begin from the time of signing informed consent and will continue throughout the entire Study Period.

x Chlorine testing will occur prior to every treatment on the AMIA APD Solution Generation System.

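### SAP 14.1.2 scores product water as one 27-parameter test, so a passing retest of a single panel counts as missing

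*SAP*

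**What the plan says.** SAP 14.1.2 lists TAMC, TYMC and endotoxins together with 24 chemical limits and applies three rules to the whole list:

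- Pass: "A test will be considered meeting specifications if all of the following parameters fall within the specified limits".
- Fail: "If any of the above parameters fall outside the limits, then the test is considered not meeting specifications".
- Missing: "If any of the above parameters were not tested, then the particular test is considered missing".

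The scored result feeds three summaries. One uses initial values; the others are "one based on retest values (as mandated per decision tree), and one based on the most recent test values". SAP section 17 labels the resulting table, 14.3.7.1, as the primary safety endpoint.

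Elsewhere the two panels are handled as separate things. They have separate rows in the schedule of events and separate testing sites in SAP 14.1.2 (both names redacted). Protocol Appendix 1, footnote u, states: "The chemical collection test sampling may occur on a different day than the product water microbiological test sampling". On follow-up of results, protocol 6.5.8 says that "corrective measures (e.g., re-culture and/or disinfection of the WD) will be based on the organism growing".

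SAP 14.1.2 also plans a met/not-met table and a descriptive table for each parameter, a full listing, and a sensitivity analysis that uses the home-installation result where Visit 1 data are missing. Protocol 10.1 says that missing values are not imputed and that all non-missing values are used.

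**The concern.** The unit of scoring does not match the unit of sampling. A culture and a chemistry sample can be taken, lost or repeated independently, but the composite needs all 27 results before it can say that a test met specification.

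Two consequences follow for a primary safety endpoint. First, a retest limited to the panel that failed leaves the other panel untested, so a clean retest cannot be shown as met in the summary that exists to report retests. Second, if one panel is lost at a visit, a fully passing other panel drops out of the composite table.

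The study is descriptive and these counts and percentages are its main product-water output. A reader of the primary table should be able to see how many failures were cleared on retest and how many valid panel results were obtained.

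**Working it through.** The plan gives no figure on this point and no sample-size calculation, so there is nothing to reproduce. The check is to count the parameters, apply the rules as written, and size the effect under stated assumptions.

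**1. Parameter count (SAP 14.1.2).** Microbiological: TAMC, TYMC, endotoxins = 3. Chemical: aluminum through total chlorine = 24. Total 3 + 24 = 27.

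**2. Scoring under the rules.** The SAP does not say whether failure or missing takes precedence, so both orders are shown.

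| Result | Failure first | Missing first |
|---|---|---|
| Initial test, all 27 tested, one culture result out | not met | not met |
| Re-culture only, passing (24 untested) | missing | missing |
| Re-culture only, failing (24 untested) | not met | missing |
| Chemistry only, all passing (3 untested) | missing | missing |
| Chemistry only, one failing (3 untested) | not met | missing |

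A passing one-panel retest is missing under either order. In the retest summary, a re-culture alone can therefore never score met.

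**3. The most-recent summary.** The SAP does not say whether most recent applies to the test or to each parameter. After an initial culture failure with passing chemistry and then a clean re-culture:

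- read per test, the latest test is the re-culture, so the visit is missing;
- read per parameter, the re-culture replaces the 3 culture results and the 24 chemistry results stand, so the visit is met.

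**4. Illustration for retests.** Inputs: 30 target completers (protocol 10.2) × 4 scheduled tests (Weeks 1, 4, 8 and 12) = 120. Assumed: 6 culture failures, all re-cultured alone, all clean, nothing else missing or failing.

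| Summary | As written, per test | Panels scored separately |
|---|---|---|
| Initial | 114/120 = 95.0% | 114/120 = 95.0% |
| Retest | 0 scorable, 6 missing | 6/6 |
| Most recent | 114/114 = 100%, 6 missing | 120/120 = 100% |

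The percentage in the most-recent row is the same. What differs is the number scored and whether the six cleared failures are visible.

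**5. Illustration for lost panels.** Assume each panel is lost independently with probability m and that everything tested passes. The composite is missing with probability 1 − (1 − m)². Exactly one panel is lost, so that a valid other panel goes unused in the composite, with probability 2m(1 − m). Out of 120:

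| m (assumed) | Missing per panel, 120m | Composite missing | Valid panels left out of composite |
|---|---|---|---|
| 2% | 2.4 | 120 × 0.0396 = 4.8 | 120 × 0.0392 = 4.7 |
| 5% | 6.0 | 120 × 0.0975 = 11.7 | 120 × 0.095 = 11.4 |
| 10% | 12.0 | 120 × 0.19 = 22.8 | 120 × 0.18 = 21.6 |

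**The case against.** **Retest content is not known.** Retests are those mandated by a sponsor decision tree that is cited but not reproduced. Protocol 6.5.8 gives re-culture only as an example, and protocol 6.5.8.5.1 lists resampling without limiting it to one panel. If every mandated retest covers all 27 parameters, the retest problem does not arise. This stands, and makes the retest part conditional. It does not touch the lost-panel part.

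**Nothing is deleted.** The individual-parameter tables and the listing keep every value, and the sensitivity analysis can fill Visit 1. This also stands: the loss is confined to the composite table. But that table is the one labelled as the primary safety endpoint, and the sensitivity analysis does not reach Weeks 4, 8 or 12.

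**A complete panel is a reasonable condition for conformity.** Declining to call an incomplete test conforming is defensible for an overall result. It does not explain why the panels are not also reported separately.

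**Stronger readings that the documents do not support.** A reader might infer that dropping cleared failures from the denominator inflates the most-recent pass rate. Compared with separate scoring it does not: 114/114 and 120/120 are both 100%. If 3 of the 6 re-cultures failed and scored not met, the figures would be 114/117 = 97.4% as written and 117/120 = 97.5% with separate scoring, so the rate as written is slightly lower. A higher rate would need failing retests to score missing, which depends on an order of precedence that the SAP does not state and is a separate question. The initial-value summary shows 114/120 in any case, so no failure is hidden.

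A reader might also extend the point to the dialysis solution and the holding bag, which use the same missing rule. The documents show no split into separately sampled panels and no one-panel retest for either. Finally, different sampling days are permitted rather than required, and different laboratories can only be inferred because the names are redacted.

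**Conclusion.** The point holds in a limited form. As written, a passing retest of one panel cannot score met in the retest summary, and it scores missing in the most-recent summary if that is read per test. A lost panel takes a fully passing other panel out of the composite primary table, but not out of the parameter tables or listings.

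The harm is lost information and fewer scorable tests. In the assumed example, six clean re-cultures yield no scorable retest, and six visits are missing from the most-recent table. With an assumed 5% loss per panel, about 11.7 of 120 composites would be missing against 6.0 for each panel alone (4.8 against 2.4 at 2%; 22.8 against 12.0 at 10%). The failure and loss rates are assumptions; the documents give none. The retest part rests on retests being limited to one panel. The most-recent part rests in addition on the per-test reading. The change is worth making because it is cheap and bears on a primary endpoint, but no conclusion of the study turns on it.

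**What to change.** In SAP 14.1.2:

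1. At each visit, report met/not met for the microbiological panel (3 parameters) and the chemical panel (24 parameters) separately, as well as the overall result.
2. Score a retest only on the panel that was retested.
3. Define most recent per panel. Form the overall most-recent result from the latest result of each panel.
4. Flag any visit where the water device was disinfected or components were replaced between the two samples being combined. The chemistry then describes the device before that intervention and the culture describes it after, and the reader should see this.

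The cost is a few lines of SAP text, added rows in Table 14.3.7.1 and the matching programming. No additional sample or visit is needed; the flag needs the dates of disinfection and component changes to be available in the data.
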